#### Anaphylactic reaction:

Administration of xenogeneic proteins may be accompanied by anaphylactic reactions that are mostly IgE mediated. The most probable time of onset, if occurring, is within 10 minutes after starting T-Guard infusions. This acute hypersensitivity reactions may be characterized by: cardiovascular collapse, cardiorespiratory arrest, loss of consciousness, hypotension, pulmonary edema especially in patients with volume overload, seizures or coma, tachycardia, pruritus, urticaria, tingling, angioedema including laryngeal, pharyngeal or facial edema, dyspnea, bronchospasm, and airway obstruction.

If an anaphylactic reaction is suspected, T-Guard administration should be discontinued immediately. Therapy should not be resumed, nor should the patient be exposed to other murine immunoglobulins or RTA-containing products.

#### Capillary Leak Syndrome (CLS):

Manifested as hypotension, fluid overload, weight gain or edema, dyspnea, anorexia, nausea, and in some cases confusion, and muscle damage. Investigative findings, may include, hypoxia, hypoalbuminemia, pulmonary edema, pleural effusion. Patients experiencing severe CLS (requiring pressors, dialysis, mechanical ventilator support) related to study treatment should have their treatment held until 72 hours after cessation of pressors, dialysis, or mechanical ventilator support.

#### Hypoalbuminemia:

Severe hypoalbuminemia is a risk for CLS. Therefore, if the albumin level is less than or equal to 1 g/dL, dosing should be held until the albumin level is greater than1 g/dL. Dosing can be based on the albumin level within 48 hours of dosing. If the treating physician feels that there has been benefit from dosing, then further dosing can be discussed with the protocol chairs.

#### Myalgia and serum CK-elevation:

There is an association of myositis with Ricin-based immunotoxicity. Therefore, patients should be monitored for signs of myositis. If patients experience muscle pain, then a serum CK should be performed. The next dosage of T-Guard should be withheld in case of a CK elevation greater than 5 times ULN. Dosing can resume if the CK decreases to less than or equal to 5 ULN and symptoms of myositis has improved to Grade 2 or less by CTCAE v.5. Dosing can proceed at the investigator's discretion if deemed in the best interest of the patient.

## Other toxicities:

Patients with another non-hematologic grade 3 or higher toxicity which is not attributable to an expected post-transplant event may have their study drug held at the attending physician's discretion. Expected post-transplant events include steroid-related toxicity and chemotherapy toxicity. T-Guard should be restarted after recovery of related toxicities to grade 2 or lower or identification of an alternative cause for these toxicities.

#### Infection:

Patients with severe infections resulting in hemodynamic instability requiring use of vasopressor medication may have study drug held at the discretion of the treating physician.

# 2.5.6 T-Guard Discontinuation

T-Guard treatment must be completed within 14 days of the first study drug dose. Patients who have missed doses may re-start T-Guard provided it is within the 14-day treatment window.

# 2.5.7 Acute GVHD Progression or Non-response

If additional systemic acute GVHD treatment, other than steroids, is added for lack of response or progression, T-Guard treatment must be discontinued and not re-instituted.

# 2.5.8 Supportive Care

# 2.5.8.1 Corticosteroid Dosing

For patients with SR-aGVHD a gradual taper of steroids rather than an abrupt discontinuation of steroids is recommended. Corticosteroid taper may be done per institutional practice or may follow the suggested schedule below for responding patients. Patients on 1 mg/kg/day may follow the taper beginning on week 2.

Week (After study initiation)	Steroid Dose
Week 1	1.5 mg/kg/day
Week 2	1.0 mg/kg/day
Week 3	0.5 mg/kg/day
Week 4	0.25 mg/kg/day
Week 5	0.2 mg/kg/day
Week 6	0.1 mg/kg/day
Week 7	0.1 mg/kg/every other day

#### 2.5.8.2 GVHD Prophylaxis Medications

Medications such as cyclosporine, tacrolimus, mycophenolate mofetil (MMF), sirolimus (if used as GVHD prophylaxis prior to the development of acute GVHD) may be continued, resumed, or increased to therapeutic doses per provider discretion, and adjusted/discontinued as necessary for renal, central nervous system (CNS) or other toxicity using institutional management guidelines. Resumption of a GVHD prophylaxis agent is not considered the addition of a second agent.

## 2.5.8.3 Topical and Ancillary GVHD Therapies

Topical treatment for acute GVHD is allowed and should be used according to institutional practices. Topical treatment, including corticosteroid creams, topical tacrolimus, oral beclomethasone or budesonide, topical azathioprine and ophthalmic glucocorticoids, is not considered as secondary systemic treatment.

Ancillary/supportive care measures for acute GVHD such as the use of anti-motility agents for diarrhea, including octreotide, is allowed at the discretion of the treating physician. Use of ursodiol to prevent/reduce gall bladder sludging or prevent hepatic transplant complications is also allowed according to institutional guidelines.

# 2.5.8.4 Other Supportive Care Guidelines

In addition to T-Guard, all patients should receive the following per institutional practice:

- Transfusion support
- Anti-infective prophylaxis against herpes viruses, *Pneumocystis jiroveci*, bacterial and fungal infections.
- Routine CMV antigenemia/viral load testing by hybrid capture or PCR based methods (with preemptive treatment in patients who develop a positive assay). CMV testing is recommended weekly through at least Day +100 post-transplant. Prophylaxis against CMV is allowed.
- In addition to the required monitoring for EBV according to the study calendar, monitoring for viral infections such as EBV, adenovirus, and HHV6 is encouraged for patients at high risk in accordance with institutional practice.

• Co-enrollment onto supportive care and infectious disease protocols will be allowed on caseby-case basis and requires approval by study chair or officer and sponsor.

# 2.5.9 Follow-Up Post Treatment Discontinuation

Patients may withdraw from treatment at any time for any reason. The reason should be documented by the study team. However, patients that have received at least one treatment dose are evaluable for all endpoints of the study and should continue with protocol-specific follow-up and data collection unless consent to study is withdrawn. Enrolled patients that do not receive any study treatment may be replaced. Patients that receive at least one treatment dose remain on study and are evaluable for all endpoints as above.

# 2.6 STUDY CONDUCT

This study will be conducted in accordance with the protocol, the BMT CTN MOP, and the following:

- Consensus ethical principles derived from international guidelines including the Declaration
   of Helsinki
- Applicable ICH Good Clinical Practice (GCP) Guidelines
- Applicable laws and regulations

The National Marrow Donor Program (NMDP) single Institutional Review Board (IRB) of Record will oversee this study and conduct the study-specific reviews as required by federal regulations and per the NMDP IRB Standard Operating Procedures (SOPs).

Site personnel will enter data in the electronic case report form (eCRF) in Advantage eClinical as described in the BMT CTN 1802 eCRF Completion Guide. Source documentation should be made available for monitoring visits, audits and regulatory inspections as described in the BMT CTN MOP.

Participating Principal Investigators bear ultimate responsibility for training of site staff as well as the scientific, technical, and administrative aspects of conduct of the protocol, even when certain tasks have been delegated to coinvestigators, sub-investigators, or staff. The PIs have a responsibility to protect the rights and welfare of participants and comply with all requirements regarding the clinical obligations and all other pertinent requirements in 21 CFR part 312. In addition to following applicable federal, state, and local regulations, investigators are expected to follow ethical principles and standards and receive training in GCP every three years and human subjects training within the past 3 years and thereafter as per institutional requirements.

# CHAPTER 3

# **3 STUDY ENDPOINTS**

## 3.1 ACUTE GVHD RESPONSE DEFINITIONS

Scoring of aGVHD response on a given day is in comparison to the patient's aGVHD staging on the day of initial T-Guard treatment. Organ staging will be assessed using the Harris criteria (Appendix C) and response will be scored as defined below:

Complete response (CR) is defined as a score of 0 for the GVHD staging in all evaluable organs. For example, for a response to be scored as CR, the patient must still be in CR on that day and have had no intervening additional systemic therapy for treatment of aGVHD.

Near-CR is defined as a score of 0 for the GI and/or liver GVHD staging, but with persistence of skin rash at less than 25% BSA (Stage 1 skin GVHD). Near CR can only occur in patients with both visceral and skin aGVHD.

Partial response (PR) is defined as improvement in one or more organs involved with GVHD symptoms without progression in others. For example, for a response to be scored as PR, the patient must still be in PR on that day and have had no intervening additional systemic therapy for treatment of aGVHD.

Mixed response (MR) is defined as improvement in one or more organs with deterioration in another organ manifesting symptoms of GVHD or development of symptoms of GVHD in a new organ.

No response (NR) is defined as absence of any improvement or progression as defined.

Patients receiving additional systemic therapy will be classified as non-responders.

Progression is defined as deterioration in at least one organ without any improvement in others.

Loss of CR or near-CR is defined as progression of aGVHD symptoms requiring additional systemic therapy; death; or if the patient develops new target organ symptoms that could qualify as being from either aGVHD or cGVHD (if the new symptoms are only associated with cGVHD then this is not considered a loss of CR).

#### 3.2 RELAPSE DEFINITION

#### Malignancy relapse is defined as follows:

Relapse is defined by either morphological or cytogenetic evidence of acute leukemia or MDS consistent with pre-transplant features, or radiologic evidence of lymphoma, documented or not by biopsy. Progression of disease applies to patients with lymphoproliferative diseases (lymphoma or chronic lymphocytic leukemia) not in remission prior to transplantation. The event is defined as increase in size of prior sites of disease or evidence of new sites of disease, documented or not by biopsy.

Acute leukemia, CML and MDS – Relapse will be diagnosed when there is:

• Reappearance of leukemia blast cells in the peripheral blood; or,

- Greater than 5% blasts in the bone marrow, not attributable to another cause (e.g. bone marrow regeneration)
- The appearance of previous or new dysplastic changes (MDS specific) within the bone marrow with or without falling donor chimerism; or
- The development of extramedullary leukemia or leukemic cells in the cerebral spinal fluid
   or
- The reappearance of cytogenetic abnormalities present prior to transplantation

#### Lymphoproliferative Diseases – Relapse or progression will be diagnosed when there is:

- Appearance of any new lesion more than 1.5 cm in any axis during or at the end of therapy, even if other lesions are decreasing in size. Increased fluoro- deoxyglucose (FDG) uptake in a previously unaffected site will only be considered relapsed or progressive disease (PD) after confirmation with other modalities. In patients with no prior history of pulmonary lymphoma, new lung nodules identified by CT are mostly benign. Thus, a therapeutic decision should not be made solely on the basis of the positron emission tomography (PET) without histologic confirmation.
- At least a 50% increase from nadir in the sum of the product diameters of any previously involved nodes, or in a single involved node, or the size of other lesions (e.g., splenic or hepatic nodules). To be considered PD, a lymph node with a diameter of the short axis of less than 1.0 cm must increase by ≥ 50% and to a size of 1.5 x 1.5 cm or more than 1.5 cm in the long axis.
- Lesions should be PET positive if observed in a typical FDG-avid lymphoma or the lesion was PET positive before therapy unless the lesion is too small to be detected with current PET systems (less than 1.5 cm in its long axis by CT).
- In addition to the criteria above, patients with chronic lymphocytic leukemia (CLL) who
  present in complete remission prior to transplantation may fulfill the relapse definition if
  there is reappearance of circulating malignant cells that are phenotypically characteristic
  of CLL.

#### *Multiple myeloma* – Clinical relapse is defined as meeting one or more of the following criteria:

- Direct indicators of increasing disease and/or end organ dysfunction (CRAB features) related to the underlying clonal plasma-cell proliferative disorder. It is not used in calculation of time to progression or progression-free survival but is listed as something that can be reported optionally or for use in clinical practice;
- Development of new soft tissue plasmacytomas or bone lesions (osteoporotic fractures do not constitute progression);
- Definite increase in the size of existing plasmacytomas or bone lesions. A definite increase is defined as a 50% (and greater than or equal to1 cm) increase as measured serially by the SPD§§ of the measurable lesion;
- Hypercalcaemia (greater than 11 mg/dL);
- Decrease in haemoglobin of greater than or equal to 2 g/dL not related to therapy or other non-myeloma-related conditions;
- Rise in serum creatinine by 2 mg/dL or more from the start of the therapy and attributable to myeloma;
- Hyperviscosity related to serum paraprotein.

For the purposes of assessing relapse free survival (RFS), if the patient is in a CR, any one or more of the following will be considered a relapse:

- Reappearance of serum or urine M-protein by immunofixation or electrophoresis;
- Development of greater than or equal to 5% plasma cells in the bone marrow;
- Appearance of any other sign of progression (i.e., new plasmacytoma, lytic bone lesion, or hypercalcaemia see above).

*Myeloproliferative Neoplasms*: Relapse from CR is defined as:

- Reappearance of bone marrow disease, including blasts, monocytic blast equivalents, or fibrosis
- New extramedullary disease, including new or reappearance of splenomegaly, hepatomegaly, skin lesions, etc.

\*Institution of any therapy to treat persistent, progressive or relapsed malignancy, including the withdrawal of immunosuppressive therapy or donor lymphocyte infusion, will be considered evidence of relapse/progression regardless of whether the criteria described above were met.

*Non-malignant Diseases*: Non-malignant diseases will be considered to have a transplant status of persistent/active disease. Graft failures will be considered recurrence.

## 3.3 PRIMARY ENDPOINT

The primary endpoint is the proportion of patients with a CR at Day 28 after start of T-Guard treatment (first infusion).

#### 3.4 SECONDARY ENDPOINTS

#### 3.4.1 Key Secondary Endpoints:

#### 3.4.1.1 Duration of Complete Response (DoCR)

DoCR is defined as the time from first observation of CR until loss of CR or the date of additional systemic therapy for treatment of aGVHD. DoCR will be evaluated both in the set of all patients who achieve a CR and only in those patients who are in CR at Day 28 post- initiation of T-Guard treatment.

#### 3.4.1.2 Overall Survival (OS)

OS will be assessed at Days 90 and 180 post initiation of T-Guard treatment. An event for this analysis is death from any cause and time will be calculated from initiation of T-Guard treatment until date of death.

#### 3.4.2 Other Secondary Endpoints:

#### 3.4.2.1 Overall Response Rate (ORR)

ORR is defined as having a complete or partial response (CR+PR). The ORR will be estimated at Days 14, 28, and 56 post T-Guard initiation.

# 3.4.2.2 Proportion of Response

The proportion of patients in each aGVHD response category will be described at Days 7, 14, 28 and 56 post initiation of T-Guard.

# 3.4.2.3 Non-relapse mortality (NRM)

Events for NRM are death from any cause other than relapse/progression of the underlying malignancy. Relapse will be considered a competing risk. Time for NRM will be from time of T-Guard initiation until the earlier of death from a non-relapse cause or relapse (competing risk). NRM will be estimated at Days 100 and 180 post initiation of T-Guard.

# 3.4.2.4 Relapse free survival (RFS)

Events for RFS are death from any cause or relapse/progression of the underlying malignancy. Time will be calculated from the initiation of T-Guard treatment until the earlier of death or relapse/progression of the underlying malignancy. RFS will be estimated at Day 180 post initiation of T-Guard.

# 3.4.2.5 GVHD-free Survival

Patients alive, in CR and without cGVHD will be considered a success for this endpoint. GVHD free survival will be estimated at Days 90 and 180 post initiation of T-Guard treatment.

# 3.4.2.6 Chronic GVHD (cGVHD)

cGVHD is defined per NIH Consensus Criteria (see Appendix D). Time will be calculated from the initiation of T-Guard treatment until the earlier of diagnosis of cGVHD or death from any cause, with death treated as a competing risk. The cumulative incidence of cGVHD at Day 180 post T-Guard initiation will be estimated and maximum severity (mild/moderate/severe) will be described.

# 3.4.2.7 Relapse/Progression of Underlying Malignancy

The cumulative incidence of malignancy relapse/progression will be estimated with death prior to relapse/progression considered a competing risk. The cumulative incidence of relapse/progression at Day 180 post T-Guard initiation will be described.

# 3.4.2.8 Incidence of Systemic Infections

All Grade 2-3 infections (as defined by the BMT CTN MOP) from initiation of T-Guard treatment will be reported by site of disease, date of onset, and severity. Incidence of systemic infections will be described in patients from the initiation of T-Guard treatment to 28 days post last dose.

# 3.4.2.9 Incidence of Toxicities

All grade 3-5 toxicities according to CTCAE v5 occurring from the initiation of T-Guard treatment to 28 days post last dose will be described.

# 3.4.2.10 Pharmacokinetics of T-Guard

A population pharmacokinetic model will be developed for T-Guard based on the SPV-T3a- RTA and WT1-RTA levels measured in samples obtained before each infusion and at the following post-infusion timepoints: 4, 5, 6, 8, and 24 hours for the first infusion, 4, 6, and 24 hours for the

second and third infusions, and 4, 6, 24 and 48 hours for the fourth infusion. The time points for blood sampling were based on the  $t_{1/2}$  and  $C_{max}$  values as determined in the previous studies. The Population PK model will be used to describe the following metrics:

- Cinf: Observed and model-predicted concentration at the end of infusion
- CL: Systemic clearance
- AUC: Model-predicted area under the curve from the start of the current infusion until the next infusion or until 48 hours following for the last infusion
- t1/2: Model-predicted terminal half-life
- Vc: Volume of the central compartment

Additionally, the impact of various factors on these measures will be evaluated, including age, weight, BSA, BMI, disease status, and anti-drug-antibodies (ADA).

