# 2.3.3 Exploratory Objectives

- 1. Describe corticosteroid-dose (measured in prednisone-equivalent) at baseline, Days 28 and 56 post initiation of T-Guard treatment.
- 2. Estimate the rate of near-CR (i.e. CR in GI and Liver with only Stage 1 Skin) at Days 28 and 56 post initiation of T-Guard treatment.
- 3. Describe discontinuation of systemic steroids by Day 180 post initiation of T-Guard treatment.
- 4. Estimate the incidence of CMV reactivation requiring treatment by Day 180 post initiation of T-Guard treatment.
- 5. Estimate the incidence of EBV-associated lymphoproliferative disorder or EBV reactivation requiring treatment with rituximab by Day 180 post initiation of T-Guard treatment.
- 6. Describe the incidence of IMP related SAEs.
- 7. Evaluate T-cell subsets and NK-cells at baseline and at Days 0, 2, 4, 6 (just prior to and 4 hours after each T-Guard infusion) and then subsequently at Days 14, 28, 56, and 180.
- 8. Evaluate aGVHD Biomarkers at baseline and at Days 7, 14 and 28 post initiation of T- Guard treatment.
- 9. Describe changes in patient-reported outcomes (PROs) from baseline to Days 28, 56 and 180 post initiation of T-Guard treatment.

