# 2.5.4 Dose and Administration of T-Guard

T-Guard will be administered at a dose of 4mg/m^2 (actual body weight) over 4 hours every 2 calendar days on Days 0, 2, 4, and 6. Infusions of T-Guard that exceed 4 hours are not considered deviations. Pauses in the infusion due to a patient reaction need to be documented.

The maximum BSA to be used in dose calculation is 2.5 m^2. If the patient's BSA is more than

2.5 m^2, the dose calculation should use 2.5 m^2. The patient's weight on the day of the first dose will determine the dose for the remaining infusions (dose adjustments for changes in weight during the treatment period will not be made).

Premedication with diphenhydramine 50 mg by mouth or 25 mg IV should be administered 30 minutes prior to each dose. For pediatric patients, the diphenhydramine dose should not exceed 1 mg/kg. Premedication with acetaminophen is permitted.

It is recommended that T-Guard be infused via a central catheter using a dedicated line or can be administered via a peripheral line, if needed. If a multi-lumen central venous catheter is used, T-Guard and crystalloid or total parenteral nutrition should be administered through different lumens of the catheter. PK samples should be drawn from the central catheter using a different lumen than the lumen used for infusion.

Before the infusion, connect the syringe with the in-line filter and luer-lock extension tube to a central venous catheter (recommended) or peripheral line. The contents of the syringe will then be administered by means of an automated infusion device, over a period of 4 hours. Once the infusion syringe is empty, the administration tubes will be flushed.

Vital signs (temperature, pulse, respiratory rate, blood pressure), should be checked at the following timepoints with each infusion: just before starting the infusion, 15 minutes after the start of the infusion, 30 minutes after the start of the infusion, then every 30 minutes during the infusion, and at 1-hour post-infusion. Deviation of +/- 5 minutes may occur for all vital sign collection timepoints.

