Infusion-related reactions are a potential risk with this medication. If the patient experiences a grade 3 or 4 infusion related reaction, the infusion should be held, and the reaction managed per institutional standards. Once the reaction has resolved the infusion can be restarted at half the rate. Subsequent infusions should be managed with an escalation in premedication based on type of reaction and initiated at the half rate. After 15 minutes, if no reactions are noted, then the infusion rate can be escalated to the full rate as tolerated.

Patients should receive a maximum of 4 doses. The minimal interval between doses is 2 days (no less than 40 hours apart). If required for logistics, a delay of up to 1 day can occur between one of the doses during the treatment course. If toxicity occurs, then dosing can be delayed until toxicity improves, but all dosing must be completed within 14 days.

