#### At Each Infusion of T-Guard Therapy

- 1. Complete acute GVHD staging and grading information including assessments of rash, diarrhea, nausea/vomiting, and bilirubin
- 2. Vital signs (temperature, pulse, respiratory rate, blood pressure) just before starting the infusion, 15 minutes after the start of the infusion, 30 minutes after the start of the infusion, then every 30 minutes during the infusion, and at 1-hour post-infusion\*. Deviation of +/- 5 minutes may occur for all vital sign collection timepoints.
- 3. Albumin and platelet count prior to each dose of T-Guard
- 4. CBC with differential
- Peripheral blood\* for immunophenotyping studies pre-infusion and at 4 hours after the start of infusion. Pre-infusion samples should be drawn prior to T-Guard administration and a window of +/- 15 minutes is allowed for the sample drawn 4 hours after the start of infusion.
- 6. Peripheral blood\* for PK at the following timepoints
  - a. 1st infusion: pre-infusion, and at 4, 5, 6, 8, and 24 hours after start of infusion
  - b. 2nd infusion: pre-infusion, and at 4, 6, and 24 hours after start of infusion
  - c. 3rd infusion: pre-infusion, and at 4, 6, and 24 hours after start of infusion
  - d. 4th infusion: pre-infusion, and at 4, 6, 24, and 48 hours after start of infusion

Pre-infusion samples should be drawn prior to T-Guard administration. A window of +/- 15 minutes for samples drawn at 4,5, or 6 hours after the start of infusion, and a window of +/-30

minutes for the sample drawn 8 hours after the start of infusion is allowed. A window of +/- 2 hours for samples drawn 24 or 48 hours after the start of infusion is also allowed. Every effort should be made to collect PK samples at all timepoints, however, the treatment schedule should not be altered to accommodate PK sampling. For example, if T-Guard administration is scheduled for a weekend and PK sampling is not possible then administration should occur on schedule. In the event weekend PK sample collection is missed, collection of PK samples should be resumed at the next T-Guard infusion. Please refer to Section 4.5 for more information regarding infusion delays.

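### Observed end-of-infusion concentration has no sample tied to the end of infusion, so infusions running more than about 15 minutes over 4 hours miss it by design, and the sampling anchor is worded inconsistently

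*Combined protocol and SAP*

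**What the plan says.** Section 3.4.2.10 names the metric as "Cinf: Observed and model-predicted concentration at the end of infusion". It places the samples "at the following post-infusion timepoints: 4, 5, 6, 8, and 24 hours for the first infusion", and Section 5.4.12 likewise describes time points after infusion. The collection instruction in Section 4.3.2 reads differently for infusion 1: "pre-infusion, and at 4, 5, 6, 8, and 24 hours after start of infusion". It uses the same start anchor for infusions 2 to 4, and so does the PK row of Appendix B. The windows are ±15 min at 4, 5 and 6 h and ±30 min at 8 h, all counted from the start.

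The nominal infusion lasts 4 h. Section 2.5.4 adds "Infusions of T-Guard that exceed 4 hours are not considered deviations", expects pauses for reactions to be documented and, after a grade 3 or 4 reaction, says "Once the reaction has resolved the infusion can be restarted at half the rate". Later infusions then begin at half rate and may go to full rate after 15 minutes as tolerated. No upper limit on duration is given.

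For immunophenotyping, Section 2.3.3 says "just prior to and 4 hours after each T-Guard infusion", whereas Section 4.3.2 counts the 4 hours from the start of infusion.

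On missed weekend sampling, Section 4.3.2 says "In the event weekend PK sample collection is missed, collection of PK samples should be resumed at the next T-Guard infusion".

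**The concern.** An observed end-of-infusion concentration needs a sample at the end of infusion. The schedule supplies one only when the infusion finishes close to 4 h. In a longer infusion, the sample that would normally serve as Cinf is drawn while drug is still running or on hold, and no rule moves it. PK is a secondary objective (Section 2.3.2), and peak concentration is part of the dose justification in Section 1.3.3. A draw taken at the wrong time cannot be replaced later.

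The mixed wording adds a second problem. In an ordinary 4 h infusion, 4 h after the start and 4 h after the end are four hours apart.

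The weekend rule, read literally, also drops weekday samples that could have been taken.

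**Working it through.** The plan gives no figure of its own on this point, so there is none to reproduce. The check compares the sampling clock with the infusion lengths that Section 2.5.4 permits.

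**1. When the infusion ends.** For a reaction at t hours, a pause of p hours and a restart at half rate, the end is t + p + 2(4 − t).
- With no pause, t = 1, 2 or 3 h gives an end at 7, 6 or 5 h.
- A later infusion at half rate for 15 min and full rate afterwards ends at 0.25 + (4 − 0.125) = 4.125 h, or 4 h 07.5 min. That is inside the 4 h window.
- A later infusion that stays at half rate throughout ends at 8 h.

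**2. Whether another window catches the end by chance.** Take end times from 4 h 15 min to 8 h 30 min, a span of 4.25 h.
- Infusion 1 has windows at 5, 6 and 8 h: (0.5 + 0.5 + 1.0)/4.25 = 47% of the span.
- Infusions 2 to 4 have only the 6 h window: 0.5/4.25 = 12%.

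These are shares of clock time, not probabilities.

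**3. How far a 4 h sample is from true Cinf.** The documents give no half-life. I assume 4 to 24 h, one compartment, and k = ln 2/half-life.
- *Half-rate restart at 2 h, no pause, end at 6 h.* With x = exp(−2k), C(4)/C(6) = (x + ½)/(x² + ½(1 + x)). Half-life 4 h: x = 0.707, so 1.207/1.354 = 0.89. Half-life 24 h: x = 0.944, so 1.444/1.863 = 0.78.
- *Constant slow rate over 8 h.* C(4)/C(8) = (1 − exp(−4k))/(1 − exp(−8k)) = 1/(1 + exp(−4k)). Half-life 4 h: 1/1.5 = 0.67. Half-life 24 h: 1/1.891 = 0.53.
- *Only the first 15 min at half rate, end at 4 h 07.5 min.* The ratio is 0.97 to 0.98, so small overruns matter little.
- *Literal post-infusion reading, draw 4 h after the end.* exp(−4k) = 0.50 (half-life 4 h) to 0.89 (half-life 24 h).

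**4. The wording, place by place.**
- Start anchor: Section 4.3.2 for both PK and immunophenotyping; the windows in Table 4.2 footnote 4, and footnote 5; the Appendix B PK row; the windows in Appendix B footnote 1, and footnote 2.
- Post-infusion or after-infusion wording for PK: Sections 3.4.2.10 and 5.4.12, and the infusion 2 to 4 clauses of Table 4.2 footnote 4 and Appendix B footnote 1.
- After-infusion wording for immunophenotyping: the Synopsis, Sections 2.3.3, 3.5.1.6 and 5.5.7, and the Appendix B immunophenotyping row, whose own footnote counts from the start.

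**5. The weekend rule.** With dosing on Days 0, 2, 4 and 6, every start weekday puts at least one infusion on a Saturday or Sunday. A Monday start gives Monday, Wednesday, Friday and Sunday. If sampling is missed at the Sunday fourth infusion, there is no next infusion at which to resume. Read literally, the Monday 24 h and Tuesday 48 h draws are then lost. The 48 h draw exists only for infusion 4, and AUC for the last infusion runs to 48 h.

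**The case against.** The strongest reply is that this is a wording mismatch plus a small gap in one descriptive metric. Much of that stands.

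- **Frequency.** The half-rate restart applies only after a grade 3 or 4 reaction. Section 1.3.2.4 reports no acute reaction above Grade 1 in the two earlier trials (7 and 20 patients). Table 1-2 does list chills in two patients under Grade 2, which is still below that trigger. Long infusions are permitted, but the documents do not suggest they will be common.
- **Bias.** A reader might infer that observed Cinf will be biased downward and that exposure will look lowest in the patients who tolerated the drug worst. The documents do not support this. Cinf is defined at the end of infusion, so a mid-infusion sample does not meet the definition. The likelier result is a missing value. The ratios above apply only if a 4 h sample is wrongly used as Cinf.
- **The rest of the PK analysis.** A reader might also infer that it is compromised. A population model can use mid-infusion samples if actual times are known, and AUC and half-life are explicitly model-predicted. Sections 2.5.3 and 2.5.4 require dosing times and reaction pauses to be recorded. No section explicitly requires stop times or rate changes in the PK data.
- **Site error.** A reader might expect sites to draw 4 h after the end, or immunophenotyping to mix two time points. Section 4.3.2 and the footnote windows consistently count from the start, so the conflict lies mainly in summary wording. Appendix B also refers to a sample guide that is not among the documents.
- **Weekend sampling.** Section 4.3.2 asks for every effort to collect all samples, so a weekend infusion is not automatically a missed one. The resumption wording is still faulty when a fourth infusion is missed.

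What the reply does not answer is that a prolonged infusion has no sample planned at its end.

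**Conclusion.** The point holds as a cheap improvement to a secondary PK metric. Any infusion ending more than about 15 min past 4 h has no end-of-infusion sample by design; a later window may catch the end by chance, mainly in infusion 1. Under the assumed half-life of 4 to 24 h and a one-compartment model, a 4 h sample used in its place would be about 78–89% of true Cinf for a half-rate restart at 2 h without a pause, and about 53–67% for a constant slow rate over 8 h. How often this will happen is unknown and probably low. The inconsistent anchor wording is certain and needs reconciling in any case. The primary endpoint, sample size and error rates are unaffected.

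**What to change.** 1. Use the start-of-infusion anchor for all nominal PK and immunophenotyping times in the Synopsis, Sections 2.3.3, 3.4.2.10, 3.5.1.6, 5.4.12 and 5.5.7, the Table 4.2 footnotes and Appendix B.
2. When an infusion is prolonged or paused, take the nominal 4 h PK sample at the actual end of infusion instead, within 15 min. The other early PK draws and the immunophenotyping draws need no re-anchoring.
3. Record actual start, stop, pause and rate-change times for the PK dataset.
4. Report observed Cinf only from end-of-infusion samples.
5. Reword the weekend rule so that sampling resumes at the next scheduled PK time point. This keeps the 24 h and 48 h draws after a weekend fourth infusion.

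The cost is a wording amendment and a few recorded times. No samples are added, and a 4 h infusion keeps the same clock times. Staff must follow the actual stop time, and the moved draw may fall later in the day. No dosing or infusion rule changes.
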